8 ANALYSIS SETS

8.1 All Subjects Set

The **All Subjects Set** will include all subjects who are randomized or receive at least 1 dose of study drug. This analysis set will be used for all individual subject data listings and disposition summary tables, unless otherwise specified.

8.2 Full Analysis Set

The **Full Analysis Set** (FAS) will include all randomized subjects who carry the intended CFTR allele mutation and receive at least 1 dose of study drug. The FAS will be used to summarize subject demographics, baseline characteristics, and for all efficacy analyses in which subjects will be analyzed according to their randomized treatment group, unless otherwise specified.

8.3 Safety Set

The **Safety Set** will include all subjects who receive at least 1 dose of study drug. The Safety Set will be used for all safety analyses in which subjects will be analyzed according to the treatment they received, unless otherwise specified.

8.4 Analysis Sets for IA

A data cutoff date will be established for the IA as the latter of at least 140 subjects complete Week 4 Visit and at least 100 subjects complete Week 12 Visit.

All subjects randomized or dosed prior to the data cutoff date will be in the scope of the IA. All data reported on or before the data cutoff date will be included in the IA.

8.4.1 Interim Full Analysis Set

The **interim Full Analysis Set** (iFAS) will include subjects in the FAS whose scheduled Week 4 Visit is on or before the data cutoff date. That is, the iFAS will include subjects in the FAS who complete the Week 4 Visit or are randomized at least 28 days before the data cutoff date.

The iFAS will be used during the IA for subject demographics, baseline characteristics, and all efficacy analyses in which subjects will be analyzed according to their randomized treatment group.

8.4.2 Interim Safety Set

The **interim Safety Set** (IA Safety Set) will include subjects in the Safety Set who complete the Week 4 Visit or receive their first dose of study drug at least 28 days before the data cutoff date.

The IA Safety Set will be used during the IA for safety analyses in which subjects will be analyzed according to the treatment they received.

9 STATISTICAL ANALYSIS

This section discusses the analyses planned for the final analysis. See Section [10.1](#) for the analyses planned for the IA.

9.1 General Considerations

The Schedule of Assessments is provided in Section 3 of CSP. The precision standards for reporting safety and efficacy variables are provided in an internal Biometrics document that specifies the programming rules including the precision for derived variables.

Continuous variables will be summarized using the following descriptive summary statistics: the number of subjects (n), mean, SD, median, minimum value (min), and maximum value (max).

Categorical variables will be summarized using counts and percentages. Percentages will be presented to 1 decimal place.

Baseline value, unless otherwise specified, is defined as the most recent non-missing measurement (scheduled or unscheduled) collected before the first dose of study drug in the Treatment Period.

Absolute change from baseline will be calculated as post-baseline value - baseline value.

Relative change from baseline will be calculated as (post-baseline value - baseline value)/baseline value.

Treatment-emergent (TE) period will include the time from the first dose of study drug in the Treatment Period until 28 days after the last dose of study drug or to the completion of study participation, whichever occurs first.

Unscheduled visits: Unscheduled visit measurements will be included in analysis as follows:

- 1) In scheduled visit windows per specified visit windowing rules
- 2) In the derivation of baseline and last on-treatment measurements
- 3) In the derivation of maximum and minimum values during TE period, and maximum and minimum change from baseline values during TE period for safety analyses
- 4) In individual subject data listings as appropriate

Visit windowing rules: The analysis visit windows for protocol-defined visits are provided in [Appendix A](#).

Incomplete/missing data will not be imputed, unless otherwise specified.

Outliers: No formal statistical analyses will be performed to detect or remedy the presence of statistical outliers, unless otherwise specified.

9.2 Background Characteristics

9.2.1 Subject Disposition

The number of subjects in the following categories will be summarized:

- All Subjects Set
- Full Analysis Set
- Safety Set
- Randomized
- Randomized but not dosed

The number and percentage (based on the FAS) of subjects in each of the following disposition categories will be summarized by treatment group and overall:

- Completed treatment
- Prematurely discontinued treatment and the reason for discontinuation
- Completed study
- Prematurely discontinued the study and the reason for discontinuation
- Rollover to open-label study

A listing will be provided for subjects who discontinued treatment or who discontinued study with reasons for discontinuation.

9.2.2 Demographics and Baseline Characteristics

Demographics and baseline characteristics will be summarized by treatment group and overall based on the FAS.

Demographic data will include the following:

- Age at baseline (in years)
- Sex (male, female)
- Ethnicity (Hispanic or Latino, not Hispanic or Latino, and not collected per local regulations)
- Race (White, Black or African American, Asian, American Indian or Alaska Native, Native Hawaiian or Other Pacific Islander, Other, and not collected per local regulations)
- Geographic region (North America, Europe [including Australia])

Baseline characteristics will include the following:

- Weight (kg)
- Height (cm)
- BMI (kg/m²)
- BMI z-score (for subjects ≤ 20 years old at Baseline)

Stratification categories (in addition to sex) will include the following:

- Age at the Screening Visit (<18, and ≥ 18 years)
- ppFEV₁ determined during the Screening Period (<70, and ≥ 70)

Disease characteristics will include the following:

- ppFEV₁ at baseline (<40, ≥ 40 to <70, ≥ 70 to ≤ 90 , and >90)
- ppFEV₁ at baseline (continuous)
- Sweat chloride at baseline (continuous)
- CFQ-R respiratory domain score at baseline (continuous)
- Prior use of dornase alfa (Yes, No)
- Prior use of azithromycin (Yes, No)
- Prior use of inhaled antibiotic (Yes, No)
- Prior use of any bronchodilator (Yes, No)
- Prior use of any inhaled bronchodilator (Yes, No)
- Prior use of any inhaled hypertonic saline (Yes, No)
- Prior use of any inhaled corticosteroids (Yes, No)

- Infection with *Pseudomonas aeruginosa* within 2 years prior to screening (Positive, Negative)

In addition, data listings will also be provided for:

- Informed consent;
- Inclusion/Exclusion criteria violation for subjects with any such violations.

9.2.3 Medical History

Medical history will be coded by using the Medical Dictionary for Regulatory Activities (MedDRA). For the FAS, medical history will be summarized descriptively by system organ class (SOC) and preferred term (PT). The corresponding data listing will also be provided.

In addition, the number of subjects reported to have had positive cultures for respiratory pathogens within the 2 years prior to screening (i.e., answered yes on the respiratory microbiology form) will be summarized for the FAS. The corresponding data listing will be provided. Hospitalization and clinic visit history in the year prior to the signing of informed consent will be listed.

9.2.4 Prior and Concomitant Medications

Medications will be coded using the World Health Organization Drug Dictionary (WHO-DD) and categorized as follows:

Prior medication: any medication that was administered during the 56 days before the first dose of study drug.

Concomitant medication: medication continued or newly received during the TE period.

Post-treatment medication: medication continued or newly received after the TE period.

A given medication may be classified as follows: prior, concomitant, post-treatment, both prior and concomitant, both concomitant and post-treatment, or prior, concomitant, and post-treatment.

If a medication has a completely missing or partially missing start/stop date and it cannot be determined whether it was taken before the first dose date of study drug, concomitantly during the TE period, or after the TE period, it will be classified as prior, concomitant, and post-treatment.

For the FAS, prior medications and concomitant medications will be summarized descriptively by: 1) treatment group and overall, preferred name (PN); and 2) treatment group and overall, anatomic class (ATC) level 1, ATC level 2, and PN. Post-treatment medications will be listed for each subject.

Details for imputing missing or partial start and/or stop dates of medication are described in [Appendix B](#).

9.2.5 Study Drug Exposure

Duration of study drug exposure (in days) will be calculated as: last dose date of study drug – first dose date of study drug + 1, regardless of study drug interruption.

Study drug exposure (in weeks) will be summarized descriptively by the number of subjects (n), mean, SD, median, min, and max. It will also be summarized in categories for Treatment Period: ≤ 1 week, $>1-\leq 2$ weeks, $>2-\leq 4$ weeks, $>4-\leq 8$ weeks, $>8-\leq 12$ weeks, $>12-\leq 16$ weeks, $>16-\leq 20$ weeks, $>20-\leq 24$ weeks, and >24 weeks, using counts and percentages. Additionally, the total study drug exposure, defined as the sum total of the study drug exposure across all subjects (in patient-weeks and patient-years), will be provided.

Exposure summaries will be based on the Safety Set, and presented by treatment group and overall.

9.2.6 Study Drug Compliance

Study drug compliance will be calculated as: $100 \times [1 - (\text{total number of days of study drug interruption}) / (\text{duration of study drug exposure in days})]$. A study drug interruption on a given day is defined as an interruption of any study drug on that day. A study drug interruption that continues through the end of the study participation (i.e., subject does not resume study drug before the end of the study participation) will not be included in the compliance calculation.

Percentage of study drug compliance will be summarized based on the FAS, and presented by treatment group and overall. Percentage of study drug compliance will be summarized descriptively by the number of subjects (n), mean, SD, median, min, and max. It will also be summarized in categories: $<80\%$ and $\geq 80\%$ using frequency tables.

In addition, percentage of tablets taken will be calculated using the following formula:

$100 \times [(\text{total number of tablets dispensed}) - (\text{total number of tablets returned})] / (\text{total number of tablets planned to be taken per day} \times \text{duration of study drug exposure in days})$. Summary similar to those for the study drug compliance will be produced based on the FAS.

9.2.7 Important Protocol Deviations

An important protocol deviation (IPD) is a deviation that may significantly affect the completeness, accuracy, or reliability of the study data or that may significantly affect a subject's rights, safety, or well-being. IPD rules will be developed and finalized prior to the IA data lock.

The protocol deviations that should be considered as potential IPDs include, but are not limited to:

- Subject was enrolled in the study despite the violation of inclusion/exclusion criteria
- Subject was less than 80% compliant with study drug for non-safety reason
- Subject received prohibited concomitant medications
- Subject received the wrong treatment or incorrect doses
- Subject remained in the study despite meeting withdrawal criteria

Occurrence of any of these events should be considered as potential IPDs, but a blinded team should categorize them as IPDs only if they have the potential to significantly affect the completeness, accuracy, or reliability of the study data or that may significantly affect a subject's rights, safety, or well-being.

IPDs (from the clinical database or from the site deviation log) will be summarized descriptively based on the FAS and presented by treatment group and overall. Additionally, IPDs will be provided in an individual subject data listing.

9.3 Efficacy Analysis

All efficacy analyses described in this section will be based on the FAS, unless otherwise specified.

9.3.1 Analysis of Primary Efficacy Variable

9.3.1.1 Definition of Variables

The primary efficacy variable is the absolute change in ppFEV₁ from baseline at Week 4. Percent predicted FEV₁ is the ratio of FEV₁ (L) and predicted FEV₁ (L), expressed as a percentage. See [Appendix C](#) for more details.

9.3.1.2 Primary Analysis

The primary analysis will be performed using a mixed-effects model for repeated measures (MMRM) with change from baseline at Day 15, Week 4, Week 8, Week 12, Week 16, and Week 24 as the dependent variable. The model will include treatment group, visit, and treatment by visit interaction as fixed effects, with continuous baseline ppFEV₁, age at screening (<18 versus ≥18 years of age) and sex (male versus female) as covariates. The model will be estimated using restricted maximum likelihood. Denominator degrees of freedom for the *F*-test for fixed effects will be estimated using the Kenward-Roger approximation². An unstructured covariance structure will be used to model the within-subject errors. If the model estimation does not converge, a compound symmetry covariance structure will be used instead. Conditional on the observed data and covariates, missing data will be assumed to be missing at random; consequently, no imputation of missing data will be performed.

The primary result obtained from the model will be the estimated treatment difference at Week 4. The adjusted means with 2-sided 95% confidence intervals and 2-sided *P* values will be provided. Furthermore, the treatment difference at each post-baseline visit obtained from the model will also be provided.

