9.1.1 Screening

The Screening Period (Day -28 through Day -1) will occur within 28 days before the first dose of study drug.

Screening assessments will be used to confirm that subjects meet the eligibility criteria. The investigator (or an appropriate authorized designee) will obtain informed consent and assent, if applicable, from each subject before any study procedure takes place.

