11.6 Efficacy

11.6.1 Spirometry

Spirometry will be performed according to the American Thoracic Society Guidelines/European Respiratory Society Guidelines¹⁰ and according to the additional guidelines that follow.

Pre-bronchodilator spirometry is defined as spirometry testing performed for subjects who have

- withheld their short-acting bronchodilators (e.g., albuterol) or anticholinergic (e.g., ipratropium bromide [Atrovent[®]]) for more than 4 hours before the spirometry assessment;
- withheld their long-acting bronchodilator (e.g., salmeterol) for more than 12 hours before the spirometry assessment; and
- withheld their once-daily, long-acting bronchodilator (e.g., tiotropium bromide [Spiriva[®]]) for more than 24 hours before the spirometry assessment.

During the Screening Period, spirometry assessments may be performed pre- or post-bronchodilator. At all other visits, all spirometry assessments should be performed pre-bronchodilator. During the Treatment Period, spirometry assessments must be performed before study drug dosing ([Section 9.6.1](#)) at approximately the same time at each visit. In the event that a subject forgets to withhold bronchodilator(s), spirometry should be performed according to the following:

- If a subject's Day 1 spirometry assessment is pre-bronchodilator, but, on a subsequent visit, the subject forgets to withhold bronchodilator use, a post-bronchodilator spirometry assessment will be obtained for that visit only, and the visit will not be rescheduled.
- If, on Day 1, the subject forgets to withhold his/her dose of bronchodilator, spirometry should be performed post-bronchodilator, and all subsequent spirometric measurements (according to the schedule of assessments in [Table 3-2](#)) should be performed post-bronchodilator.
- Each spirometry assessment will be recorded in the source documents as pre- or post-bronchodilator.

All sites will be provided with spirometers to be used for all study assessments. Spirometry data will be transmitted to a centralized spirometry service for quality review. The investigator's assessment of the spirometry results will be used for the screening assessment and determination of eligibility.

See [Section 10.7.1](#) for information about access to spirometry results.

The measured spirometric values listed below will be converted to percent predicted values using the standard equations of GLI.⁹

- FEV₁ (L)

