7.3 Randomization

Subjects will be randomized (1:1) to the VX-445/TEZ/IVA arm or to the triple placebo arm. Randomization will be stratified by ppFEV₁ determined during the Screening Period (<70 versus ≥ 70), age at the Screening Visit (<18 versus ≥ 18 years of age), and sex (male versus female).

An interactive web response system (IWRS) will be used to assign subjects to treatment. The randomization code list will be produced by Vertex Biometrics or a qualified randomization vendor.

Randomization will occur before the first dose of study drug during the Treatment Period and may occur on either Day 1 or Day -1.

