10.1.3.1 Analysis of Primary Efficacy Variable

The analysis of the primary efficacy variable of absolute change in ppFEV₁ from baseline at Week 4 will be performed using an MMRM with change from baseline at Day 15 and Week 4 as the dependent variable. The model will include treatment group, visit, and treatment by visit interaction as fixed effects, with continuous baseline ppFEV₁, age at screening (<18 versus ≥ 18 years of age) and sex (male versus female) as covariates. The model will be estimated using restricted maximum likelihood. Denominator degrees of freedom for the *F*-test for fixed effects will be estimated using the Kenward-Roger approximation². An unstructured covariance structure will be used to model the within-subject errors. If the model estimation does not converge, a compound symmetry covariance structure will be used instead. Conditional on the observed data and covariates, missing data will be assumed to be missing at random; consequently, no imputation of missing data will be performed.

The sensitivity analysis based on the multiple imputation (Section 9.3.1.4) will be performed during the IA, if $\geq 10\%$ of the subjects have missing change in ppFEV₁ at Week 4 in any treatment group. However, since the analysis model uses the change from baseline at Day 15 and Week 4 as the dependent variable, the primary timepoint for imputation will be Week 4 and only data up to the Week 4 Visit will be used in the imputation.

Subgroup analyses of the primary efficacy variable will also be performed during the IA in a manner similar to that of the primary analysis (Section 9.3.1.5) for each of the following subgroups using data up to the Week 4 Visit:

- Age at screening (<18, ≥ 18 years)
- Percent predicted FEV₁ at baseline (<70, ≥ 70)
- Sex (male, female)
- Geographic region (North America, Europe [including Australia])

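### The ppFEV₁ models omit screening ppFEV₁, which is a stratification factor and a second pre-treatment value: a modest, avoidable loss of precision

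*SAP*

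**What the plan says.** **Randomization.** Protocol 9.2 and SAP 7.3 use three factors. Allocation is "stratified by ppFEV₁ determined during the Screening Period", split at 70, and also by age (<18 versus ≥18 years) and sex.

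**Model.** The final MMRM (SAP 9.3.1.2, protocol 12.3.3.1.1) carries the age stratum and sex. Its only lung-function covariate is in the phrase "with continuous baseline ppFEV₁, age at screening". The interim analysis (SAP 10.1.3.1, protocol 12.3.3.2.1) is an "MMRM with change from baseline at Day 15 and Week 4 as the dependent variable", with the same covariates.

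**Baseline.** SAP 9.1 defines it as "the most recent non-missing measurement (scheduled or unscheduled) collected before the first dose of study drug". Protocol Tables 3-1 and 3-2 schedule spirometry at Screening and again on Day 1, so baseline is normally Day 1 and the screening value is a separate measurement.

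**Elsewhere.** The first key secondary endpoint, change through Week 24, uses the primary model unchanged (SAP 9.3.2.2). SAP 9.3.1.3 plans no supportive analysis of the primary endpoint. SAP 9.3.4.3 does use screening ppFEV₁ (<70/≥70), with age and sex, to stratify the Wilcoxon test of event duration. No reason is given for treating the ppFEV₁ models differently.

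**The concern.** Two of the three stratification factors are in the ppFEV₁ models as randomized. The third is represented only by a later measurement of the same quantity. A single spirometry reading is an imperfect measure of a subject's usual level, and a second pre-treatment reading removes part of that error.

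What is at stake is the width of the ppFEV₁ confidence intervals: at the interim, which may rest on about 70 subjects per arm and can support a regulatory submission; at the final analysis; for the average through Week 24; and in the subgroup models, which are fitted separately within each category (SAP 9.3.1.5).

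**Working it through.** **1. The plan's own power.** Inputs from SAP 7.2: SD 7, difference 5.0, 70 per arm, 5% dropout, two-sided α 0.044.

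- Interim: 70 × 0.95 = 66.5 per arm. Noncentrality = 5 / (7 × √(2/66.5)) = 4.12. Power is 98.1% (noncentral t) or 98.2% (normal), against about 98% stated.
- Final, α 0.01: above 99.9% with 180 × 0.95 = 171 or 180 × 0.90 = 162 per arm, against about 99% stated.
- Through Week 24, α 0.05, 162 per arm: above 99.9%, against about 99% stated.

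The stated figures are met or exceeded.

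**2. Equal correlation r between all visits (assumption).** The residual variance of the Week 4 value, as a share of its total, is 1 − r² given Day 1 alone and (1 − r)(1 + 2r)/(1 + r) given Day 1 and screening. The ratio is (1 + 2r)/(1 + r)².

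| r | Variance ratio | SE reduction |
|---|---|---|
| 0.5 | 0.889 | 6% |
| 0.7 | 0.830 | 9% |
| 0.8 | 0.802 | 10% |
| 0.9 | 0.776 | 12% |

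**3. SD of change held at the plan's 7.** Let e² be visit-to-visit noise, and h² a lasting subject-level shift after Day 1 that no pre-treatment value can predict. Then 2e² + h² = 49. Let f be the noise share, so e² = 49f/2 and h² = 49(1 − f). Assumed: SD of one pre-treatment value 12, 14.4 or 16; f from 0.25 to 1; extra screening noise of SD 0 or 4 for mixed bronchodilator state.

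Example with SD 14.4, f = 0.5 and no extra noise:

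- e² = 12.25, h² = 24.5, stable variance b² = 207.36 − 12.25 = 195.11.
- Week 4 variance = 195.11 + 12.25 + 24.5 = 231.86.
- Given Day 1: 231.86 − 195.11²/207.36 = 48.3, SD 6.95.
- Given both: 231.86 − 195.11²/(195.11 + 12.25/2) = 42.7, SD 6.53.
- Ratio 0.884, so the SE falls by 6%.

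Reduction in SE (%), with ranges over the three SDs. The average through Week 24 uses five visits, since the plan leaves Day 15 out of it.

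| f | Week 4 | Week 4, extra noise | Through Week 24 | Through Week 24, extra noise |
|---|---|---|---|---|
| 0.25 | 3.0–3.1 | 1.3 | 3.3–3.4 | 1.4–1.5 |
| 0.50 | 5.7–6.1 | 3.4–3.6 | 7.3–7.7 | 4.3–4.5 |
| 0.75 | 8.4–9.0 | 5.6–6.1 | 12.5–13.3 | 8.3–9.0 |
| 1.00 | 10.9–12.0 | 7.9–8.8 | 20.3–21.8 | 14.5–15.7 |

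Interim power with these residual SDs moves from 98.1–98.8% to 98.4–99.7%.

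**4. Simulation.** ANCOVA at Week 4, 171 per arm, screening ppFEV₁ 40 to 90, allocation balanced within the <70/≥70 strata, SD 14.4, true difference 5, 2,000 runs. Mean model SE:

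| Setting | Baseline only | Plus stratum | Plus continuous screening |
|---|---|---|---|
| f = 0.5 | 0.7495 | 0.7400 (−1.3%) | 0.7076 (−5.6%) |
| f = 1.0 | 0.7259 | 0.6979 (−3.9%) | 0.6488 (−10.6%) |
| f = 0.5, extra noise | 0.7484 | 0.7410 (−1.0%) | 0.7256 (−3.0%) |

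The baseline-only model gave mean estimates of 5.015, 5.005 and 4.999, so there is no sign of bias. Its empirical SDs were 0.7665, 0.7124 and 0.7640. These are within about 2.3% of the model SEs and on both sides of them, while the simulation error of an SD is about 1/√4000 = 1.6%. Nothing here suggests that the planned model understates its SE.

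**The case against.** The strongest reply is that the plan already adjusts for the stratified characteristic. Continuous Day 1 ppFEV₁ carries most of what the <70/≥70 split knows, so the planned analysis is valid and adding the stratum gains little. This stands.

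Next, nothing that will be decided depends on it. Power for ppFEV₁ is about 98 to 99% as stated, and the sample size was set by the number of pulmonary exacerbations (SAP 7.2), which this change does not help. The assumed difference of 5.0 is also cautious beside the Phase 2 result in protocol 9.3.2 (mean change 13.8 on the 200 mg triple combination, 0.0 on placebo). This stands too: the gain is in interval width.

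Third, screening is the least comparable spirometry in the trial. Protocol 11.6.1 says: "During the Screening Period, spirometry assessments may be performed pre- or post-bronchodilator", whereas later visits should be pre-bronchodilator. It can fall up to 28 days before dosing, with a possible two-week extension (protocol 9.1.1 and 9.1.1.3). This lowers the gain, as the extra-noise columns show, but it cannot bias a randomized comparison.

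Fourth, screening assessments may be repeated once and subjects rescreened once (protocol 9.1.1.1 and 9.1.1.2), so the covariate needs a definition. That is a matter of wording.

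**Conclusion.** The omission is real and costs a modest amount of precision. Continuous screening ppFEV₁ would lower the Week 4 SE by about 1 to 12% and the through-Week-24 SE by about 1 to 22%; the low ends reflect mixed bronchodilator state at screening. The stratum alone is worth about 1 to 4% at Week 4. These ranges rest on assumed between-subject SDs, noise shares and correlations. The documents supply only the SD of change.

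Four stronger readings are tempting, and the documents do not support them.

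- *That omitting a stratification factor biases the estimate or inflates type I error.* The model adjusts for the same characteristic, the simulated estimates centre on the true value, and omitting a stratification factor tends, if anything, to make the test slightly conservative.
- *That the change is worth about a quarter more subjects.* At r = 0.8 to 0.9 the equal-correlation formula gives 1/0.802 = 1.25 to 1/0.776 = 1.29. That treats all within-subject variation as visit noise and screening as being as good as Day 1. At the low end (variance ratio 0.974) it is 1/0.974 = 1.03.
- *That the SAP uses the screening stratum only descriptively.* The Wilcoxon test in SAP 9.3.4.3 uses it.
- *That every subgroup model is a small-sample one.* SAP 9.3.1.5 lists 11 two-category factors, hence 22 fits. It gives no sizes and cautions only about cases where numbers are small. The interim uses four of the factors.

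This is a free improvement to a valid analysis.

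**What to change.** Before treatment unblinding, add continuous screening ppFEV₁ next to baseline ppFEV₁ in SAP 9.3.1.2 and 10.1.3.1 and in protocol 12.3.3.1.1, and align the synopsis. Protocol 12.3.3.2.1 refers back to the final model and follows. Define the covariate as the value used for stratification, which settles repeat and rescreened measurements. Carry it into the through-Week-24 and subgroup models, which already inherit the primary model. Leave the endpoint and the baseline definition as they are.

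If the primary model can no longer be changed, pre-specify the adjusted model as a supportive analysis in SAP 9.3.1.3, which is now empty.

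The cost is one degree of freedom and a few lines of wording. The value is already collected for eligibility and stratification, so there are no new visits, procedures or data.
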